**PROTOCOL SYNOPSIS**

STUDY TITLE	A phase 3, open-label, randomized, multicenter, 12 months, efficacy and safety study of weekly MOD-4023 compared to daily Genotropin ® therapy in pre-pubertal children with growth hormone deficiency.		
PROTOCOL NO.	CP-4-006, Amendment 2, 27-APR-2018		
IND NO.	CCI	EUDRACT NO.	2016-003874-42
CLINICAL SITES	The study will be conducted in approximately 30-40 countries at approximately 200 clinical sites.		
STUDY PHASE	3		
THERAPEUTIC INDICATION	Treatment of children with growth failure due to growth hormone deficiency (GHD).		
STUDY PRIMARY OBJECTIVE	To demonstrate that weekly MOD-4023 administration is non-inferior to daily Genotropin administration.		
STUDY SECONDARY OBJECTIVES	
 
• To evaluate the safety and tolerability of weekly MOD-4023 administration.
 
• To demonstrate successful operation (single injection) of the MOD-4023 single patient use, multi-dose, disposable pre-filled pen (PEN).
 
• Evaluation of participant and observer feedback on MOD-4023 device usability.
 
• To confirm the correct operation of devices returned for evaluation.
 
		
LT-OLE OBJECTIVE	To demonstrate long term (LT) safety and efficacy of MOD-4023 in an open-label extension (OLE).		
OTHER OBJECTIVES	To evaluate the effect of weekly MOD-4023 and daily Genotropin ® administration on quality of life (QoL), as measured by the QoLISSY (Quality of Life in Short Stature Youth) in a specific number of countries (determined by availability of validated translated tools) during the first 12 months of treatment.		

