
STATISTICAL ANALYSIS:
	
Details on the statistical methods will be provided in a Statistical Analysis Plan (SAP) prior to database lock.
 
The aim of the present study is to demonstrate that in terms of annual HV at 12 months (primary efficacy endpoint), weekly MOD-4023 is non-inferior to daily Genotropin® administration by a non-inferiority margin of 1.8 cm/year.
 
With <math>\mu_M</math> and <math>\mu_C</math> representing the mean annual HV at 12 months for the MOD-4023 and the Genotropin® (Control) group, respectively, the following hypotheses will be tested:
 
Null hypothesis <math>H_0</math>: <math>\mu_M < \mu_C - 1.8</math> cm/year;
 
Versus (vs.)
 
Alternate hypothesis <math>H_1</math>: <math>\mu_M \geq \mu_C - 1.8</math> cm/year
 
Non-inferiority will be concluded for the primary efficacy endpoint if the lower bound of the 2-sided 95% CI for the mean treatment difference (MOD-4023 – Genotropin®) is <math>\geq -1.8</math> cm/year.
 
Primary Efficacy Analysis: The CI for the difference of means between the 2 treatments will be derived from an analysis using Analysis of Covariance (ANCOVA). The ANCOVA model will include the stratification classes for treatment, age group, peak hGH value during stimulation test, region and gender, and Baseline Ht SDS as a covariate. The determination of non-inferiority will be based on least squares means for the 2 treatments from the ANCOVA and the 95% CI of the differences between the treatments.
 
Summary statistics for HV at end of treatment and for absolute change in HV from Baseline to end of treatment, will be presented by treatment group (and further stratified by factors used in the ANCOVA model).
 
Secondary Analyses: Annualized HV after 6 months of treatment, and change (from Baseline) in Ht SDS at 6 and 12 months will be summarized with descriptive statistics. These 3 endpoints will each be analyzed using a similar ANCOVA model as used for the primary endpoint, with terms for treatment and the randomization strata (age, peak hGH value during stimulation test, region), gender and baseline value for each endpoint of interest. The model-derived least square means and standard error (SE) will be used to construct 95% CI for the difference between treatment groups. These analyses are considered as supportive efficacy analyses.
 
Change in BM, calculated as BA/CA at the end of 12 months, compared to

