
Effective Date: Date of final electronic approval

Baseline will be characterized with descriptive statistics (mean, SD, and 95% CI) for each treatment group.

**Primary Efficacy Sensitivity Analysis:** The ANCOVA-based primary efficacy analysis will be repeated using the modified intent-to-treat (mITT) set and the per protocol (PP) set.

The ANCOVA-based primary efficacy analysis will be repeated on the full analysis set using last observation carried forward (LOCF) in place of multiple imputation for the handling of missing data.

OAT and PAT (USA Only)

OAT and PAT results will be summarized by using descriptive statistics.

Proportion and counts of successful single injections out of total number of single injections using the MOD-4023 PEN in USA patients at Wks 1, 2, 3, 4, 5, and 6, based on the PAT will be reported. Similarly, counts and proportion of successful single injections out of total number of single injections using the MOD-4023 PEN in USA patients at Wk 1, based on the OAT will be reported. Details on the criteria constituting a successful single injection based on OAT and PAT, along with statistical methods to be used for descriptive summaries will be included in the SAP.

Comments on the PAT and OAT related to successful or unsuccessful injection attempts

The written comments provided on the PAT and OAT for successful or unsuccessful injection attempts will be listed. Any other written comments will also be listed.

Information gained by inspection of returned devices

Summary of the information gathered by inspecting the returned devices will be reported.

The QoLISSY core total score at Baseline, 12 months and change from Baseline to month 12, for each group will be summarized using descriptive statistics. This will be done for specific countries as listed in the [Appendix L](#).

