#### 8.4.5 Additional Endpoints

- Proportion of successful single injections out of total number of single injections using the MOD-4023 PEN in US patients at Wks 1, 2, 3, 4, 5, and 6, based on the PAT.
- Proportion of successful single injections out of total number of single injections using the MOD-4023 PEN in US patients at Wk 1, based on the OAT.
- Comments on the PAT related to successful or unsuccessful injection attempts.
- Comments on the OAT related to successful or unsuccessful injection attempts.
- Information gained by inspection of returned devices.
- QoL endpoint measured by the QoLISSY core questionnaire at Baseline and month 12 at specific countries per [Appendix L](#).

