#### 8.6.1 Secondary Endpoint Analyses

A similar ANCOVA model as used for the primary endpoint will be used to analyze:

- annualized HV at 6 months;
- change in Ht SDS at 6 months;
- change in Ht SDS at 12 months.

Least square mean estimates for the 2 treatments and the 95 % CI of the difference between the treatments will be presented.

Descriptive statistics will also be reported for each of these endpoints.

Descriptive statistics (including univariate 95 % CI) will be reported for BM observed and change from Baseline to 12 months.

Descriptive statistics will be reported for HV and Ht SDS at each visit.

Series plots of mean values +/- SE will be reported for HV and Ht SDS by visit and treatment.

ANCOVA-based statistics will be reported by the categorical terms used in the ANCOVA model: age group, gender, peak GH levels, and region.

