#### Quality of Life Questionnaire

The 3 dimensions (physical, social, and emotional) of the QoLISSY questionnaire will be calculated individually and as a combined core total score based on the QoLISSY scoring manual. This core score is calculated as the sum of the means of these 3 dimensions and divided by 3. All scores will be transformed from raw scores to 0 to 100 scores.

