**APPENDIX L: QOL QUESTIONNAIRE**

The QoLISSY questionnaire will be completed at Visits 2 and 8 by patients with the support of their parents/caregiver.

For patients between the age of 3-7 and 0 days, a Parent Questionnaire will be used.

For patients above and including the age of 7 and 0 days, a Child Questionnaire will be encouraged to be used.

The questionnaires are provided in the following order.

The QoLISSY questionnaire will only be filled in the following countries using a validated translated tool:

USA, Australia, New Zealand, Belarus, Russia, Ukraine, France, United Kingdom (UK), Germany, Spain, Italy, Argentina, Chile, Brazil.

Effective Date: Date of final electronic approval

IDENTIFIER/ SUBJECT NUMBER: \_\_\_\_\_

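### The protocol sets an objective on the effect of the two regimens on quality of life but specifies only per-arm descriptive statistics for QoLISSY, with no between-arm difference or interval

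*Protocol*

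**What the plan says.** The objective, under Other Objectives in the Protocol Synopsis and in Section 2, begins "To evaluate the effect of weekly MOD-4023 and daily Genotropin" and concerns quality of life measured by QoLISSY in selected countries. Section 8.4.5 lists the "QoL endpoint measured by the QoLISSY core questionnaire at Baseline and month 12 at specific countries". Section 5.11 places the questionnaire at Visits 2 and 8. Appendix L names 14 countries and says: "The QoLISSY questionnaire will only be filled in the following countries using a validated translated tool".

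Two places describe the analysis:

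- Protocol Synopsis, Statistical Analysis: the core total score at baseline, at 12 months and the "change from Baseline to month 12, for each group will be summarized using descriptive statistics".
- Section 8.6.4: scoring only. "This core score is calculated as the sum of the means of these 3 dimensions and divided by 3", with all scores rescaled to 0 to 100.

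Neither gives a model, a contrast between arms or an interval.

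Other main-study endpoints are specified more fully. For 6-month height velocity and for change in height SDS at 6 and 12 months, the Synopsis says "These 3 endpoints will each be analyzed using a similar ANCOVA model as used for the primary endpoint", and Section 8.6.1 adds: "Least square mean estimates for the 2 treatments and the 95 % CI of the difference between the treatments will be presented". For change in bone maturation the Synopsis reads "Baseline will be characterized with descriptive statistics (mean, SD, and 95% CI) for each treatment group".

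**The concern.** The objective asks about the effect of two regimens that were allocated at random, but the planned output is one column of summaries per arm. A reader interested in the regimens must subtract one mean change from the other. The protocol promises no interval for the result and no use of the baseline score.

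Both arms receive active growth hormone. A change within one arm therefore mixes treatment-related growth, a year of ageing and whatever the regimen contributes. Only the contrast between arms separates the regimen from the rest, and side-by-side columns invite the reader to interpret each arm's change on its own.

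Country is fixed before randomisation, so a contrast within the 14 QoL countries is still a randomised comparison. The data to make it will already exist. If the contrast is not written down in advance, anyone who later wants it must choose the estimator and covariates after seeing the results.

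**Working it through.** **Plan's own figures.** The protocol states no sample size, power or precision for QoLISSY, so there is no QoL figure to reproduce. Its sample size for height velocity does reproduce: 2 × 2.5² × (1.96 + 0.84)² / (1.8 − 0.8)² = 98, or 99 per arm with unrounded quantiles and rounding up, against 100 stated. Power at 100 per arm is 0.807 against 0.80 stated. This does not bear on the QoL point.

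**What the protocol specifies, by endpoint.**

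| Endpoint | Between-arm difference | Interval named |
|---|---|---|
| 6-month HV; change in Ht SDS at 6 and 12 months | Yes, ANCOVA | 95% CI of the difference |
| Change in bone maturation | No | 95% CI per arm |
| IGF-1, IGFBP-3 | No, stated outright | None |
| QoLISSY core total score | Not mentioned | None |

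**Gain from baseline adjustment.** Let the score have the same SD σ at both visits, correlation ρ between visits, and n evaluable children per arm. None of σ, ρ or n is in the documents, so all are assumptions.

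- Unadjusted difference in mean changes: variance = (2/n) · 2σ²(1 − ρ).
- Baseline-adjusted difference: variance = (2/n) · σ²(1 − ρ²), ignoring the other covariates and lost degrees of freedom.
- Ratio = (1 − ρ²) / [2(1 − ρ)] = (1 + ρ)/2. The CI width ratio is its square root.

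| Assumed ρ | Variance ratio | Width ratio | CI narrower by |
|---|---|---|---|
| 0.3 | 0.65 | 0.81 | 19% |
| 0.5 | 0.75 | 0.87 | 13% |
| 0.7 | 0.85 | 0.92 | 8% |

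**How informative the interval could be.** The 95% half-width in units of σ is 1.96 · √(2/n) · √(1 − ρ²) with adjustment, and 1.96 · √(2/n) · √(2(1 − ρ)) for the difference in changes.

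| Assumed n per arm | Adjusted, ρ = 0.3 / 0.5 / 0.7 | Difference in changes, ρ = 0.3 / 0.5 / 0.7 |
|---|---|---|
| 30 | 0.48 / 0.44 / 0.36 | 0.60 / 0.51 / 0.39 |
| 50 | 0.37 / 0.34 / 0.28 | 0.46 / 0.39 / 0.30 |
| 70 | 0.32 / 0.29 / 0.24 | 0.39 / 0.33 / 0.26 |
| 100 | 0.26 / 0.24 / 0.20 | 0.33 / 0.28 / 0.22 |

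The adjusted half-width runs from about 0.48 to 0.20 SD. The last row is close to a ceiling, because 100 per arm is the number expected after dropout across all countries.

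**Features of the QoL data that the model must respect.** No country in Appendix L is India or Vietnam, so region has two levels here, not three. Children below 7 years have the parent form, and from 7 years the child form is encouraged (Section 5.11, Appendix L). The age stratum splits at almost the same point, so the age-group term largely captures the form used at baseline. It does not identify a child who turns 7 during the year and may have a parent-reported baseline and a self-reported Month-12 score.

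**The case against.** The case against asking for more is substantial.

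- **The governing document is not available.** The protocol defers statistical detail to a main-study SAP. The SAP supplied covers the extension only and contains no QoL analysis. A reader might infer that the trial will yield no between-arm QoL estimate. The documents do not support that; they show only that the protocol specifies none. This limit stands.
- **QoL ranks low and has no hypothesis.** It is an other objective, its wording names both treatments without saying they will be compared, and the endpoint is the score at two visits. Bone maturation and the biochemical markers are secondary endpoints and are also descriptive. This is fair, and it is why the point is minor. However, for the biochemical markers the Synopsis expressly rules out a between-arm comparison. For QoL it is silent, so no reasoned omission is visible.
- **The raw changes already carry the answer.** A reader might infer that two unadjusted within-arm changes cannot estimate the treatment effect. That is wrong: under 1:1 randomisation their difference is unbiased, and selecting by country does not alter this. If N, mean and SD of change are tabulated, an unadjusted interval can be worked out by hand. Adjustment adds precision; it does not remove bias.
- **The instrument is about height.** A reader might infer that QoLISSY would show directly what fewer injections are worth to a child. All 22 core items printed in Appendix L concern height and its social and emotional consequences, and none asks about injections. Any effect of injection frequency would be indirect. Nor is QoL the only patient-reported information: injection-site pain is rated at least weekly in both arms (Section 5.8.2), and participant feedback on the device is a secondary objective, although it covers MOD-4023 users in the USA only.

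What survives is narrow: the plan collects randomised data on a stated objective and does not say that the contrast between arms will be reported with an interval.

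**Conclusion.** The point holds as a low-cost improvement to the analysis plan. As far as the protocol goes, the QoL objective is served only by per-arm description. Reporting a baseline-adjusted difference would supply an interval that the protocol does not promise, about 8% to 19% narrower than one from unadjusted changes. That range assumes equal SDs at the two visits and a correlation of 0.3 to 0.7; mixing parent and child reports could lower the correlation. With 30 to 100 evaluable children per arm, also assumed, the half-width would be roughly 0.20 to 0.48 SD, so the result would be descriptive of plausible effects and not a basis for a claim.

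Nothing here touches the primary non-inferiority conclusion. If the main-study SAP already contains such a contrast, the point closes.

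**What to change.** In the QoLISSY paragraph of the Synopsis and in Section 8.6.4 (and the main-study SAP, before database lock), keep the descriptive table and add an exploratory analysis along these lines:

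- ANCOVA of the Month-12 core total score with treatment, baseline core total score, age group, peak GH class, region (two levels in the QoL countries) and gender.
- Report the least squares mean difference with its 95% CI, without a hypothesis test, and the number of evaluable children in each arm.
- Report by arm how many children changed from the parent to the child form between visits. Repeat the analysis without them, or with form as a term. Because the child form is encouraged and not required, the form used at Month 12 is chosen after randomisation, so this is a sensitivity check only.
- State beside the result that the score is patient- or parent-reported in an open-label trial.

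The cost is one more model using code already needed for the auxology endpoints, with no added patients, visits or data. The small downside is one further exploratory comparison of an open-label score.

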**Biochemical Endpoints**

IGF-1, IGF-1 SDS, IGFBP-3 and IGFBP-3 SDS will be summarized descriptively by visit. Statistical comparisons between treatment groups are not planned. Incidence of IGF-1 SDS >2.0 will be summarized at each visit and in total as percentage of total samples.

Safety data will be reported mainly using descriptive summaries for treatment emergent AEs and laboratory values that fall outside of pre-determined ranges. Both listings and tabular summaries will be reported for all safety endpoints.

LT-OLE:

The assessment of safety and efficacy (auxology/clinical and biochemical endpoints) during the LT-OLE will be based on descriptive statistics and summarized by patient's treatment in the treatment period and overall. No hypothesis testing will be performed. The descriptive statistics will include means, standard deviations, quartiles/ranges for continuous variables, and counts with percentages for categorical data. 95% CI will be used to further describe the clinical endpoints. A separate SAP for the LT-OLE will be provided.

## GLOSSARY

Abbreviation	Definition
µg	Microgram
Ab	Antibody
ACTH	Adrenocorticotrophic Hormone
ADHD	Attention-Deficit/Hyperactivity Disorder
AE	Adverse Event
AIDS	Acquired Immunodeficiency Syndrome
ALT	Alanine Aminotransaminase (SGPT)
ANCOVA	Analysis of Covariance
AST	Asparate Transaminase (SGOT)
BA	Bone Age
BM	Bone Maturation
BMI	Body Mass Index
BP	Blood Pressure
BUN	Blood Urea Nitrogen
CA	Chronological Age
CBC	Complete Blood Count
CFR	Code of Federal Regulations
CI	Confidence Interval
cm	Centimeter
CNS	Central Nervous System
CPK	Creatinine Phosphokinase
CrCL	Creatinine Clearance
CRH	Corticotropin Releasing Hormone
CRO	Contract Research Organization
CS	Clinically Significant
CT	Computed Tomography
CTP	C-terminal Peptide
day 4(-1)	Day 3 or 4 Post-injection
DBPC	Double-Blind Placebo-Controlled
DDAVP	Desmopressin
dL	Deciliter
DMP	Data Management Plan
DSMB	Data Safety Monitoring Board
EC	Ethics Committee
ECG	Electrocardiogram
EDC	Electronic Data Capture
eCRF	Electronic Case Report Form
EMA	European Medicinal Agency

Effective Date: Date of final electronic approval

Abbreviation	Definition
EOS	End of Study
ET	Early Termination
EU	European Union
FAS	Full Analysis Subset
FDA	Food and Drug Administration
FFA	Free Fatty Acids
FSH	Follicle-Stimulating Hormone
FT4	Free Thyroxine
GCP	Good Clinical Practice
GFR	Glomerular Filtration Rate
GGT	Gamma-Glutamyl Transferase
GH	Growth Hormone
GHD	Growth Hormone Deficiency
GHR	Growth Hormone Receptor
GI	Gastrointestinal
GLP	Good Laboratory Practices
GRS	Growth Hormone Research Society
H 0	Null Hypothesis
H 1	Alternative Hypothesis
HbA1C	Glycated Hemoglobin (Hemoglobin A1c)
hCG	Human Chorionic Gonadotropin
HCT	Hematocrit
HDL	High Density Lipoproteins
HGB	Hemoglobin
hGH	Human Growth Hormone
HIV	Human Immunodeficiency Virus
HV	Height Velocity
HV SDS	Height Velocity Standard Deviation Score
Ht	Height
IB	Investigator's Brochure
ICF	Informed Consent Form
ICH	International Conference on Harmonisation
IEC	Independent Ethics Committee
IGFBP-3	IGF-1 Binding Protein 3
IGF-1	Insulin-like Growth Factor-1
IM	Intramuscular
IND	Investigational New Drug
INN	International Nonproprietary Name
INR	International Normalized Ratio (for blood clotting time)
IP	Investigational Product

Effective Date: Date of final electronic approval

Abbreviation	Definition
IRB	Institutional Review Board
IRT	Interactive Response Technology
ISF	Investigator's Site File
ITT	Insulin Tolerance Test
IV	Intravenous
kg	Kilogram
L	Liter
LDH	Lactate Dehydrogenase
LDL	Low Density Cholesterol
LFT	Liver Function Test
LH	Luteinizing Hormone
LOCF	Last Observation Carried Forward
LP(a)	Lipoprotein (a)
LT	Long term
m	Meter
MCH	Mean Cell Hemoglobin
MCHC	Mean Cell Hemoglobin Concentration
MCV	Mean Corpuscular Volume
MedDRA	Medical Dictionary for Regulatory Activities
mg	Milligram
min.	Minute
mITT	Modified Intent-to-Treat
mL	Milliliter
MM	Medical Monitor
MoH	Ministry of Health
mmol	Millimole
MRI	Magnetic Resonance Imaging
mSV	Millisievert
N	Number
ng	Nanogram
nmol	Nanomole
No.	Number
NOAEL	No Observed Adverse Effect Level
OAT	Observer Assessment Tool
OBL	OPKO Biologics Ltd.
OLE	Open Label Extension
PA	Posterior to Anterior
PAT	Participant Assessment Tool
PD	Pharmacodynamics

Effective Date: Date of final electronic approval

Abbreviation	Definition
PEN	Single patient use, multi-dose, disposable pre-filled pen containing 20 or 50 mg/mL MOD-4023
PI	Principal Investigator
PK	Pharmacokinetic
PP	Per Protocol
PT	Prothrombin Time
PT	Preferred Term
PTT	Partial Thromboplastin Time
QA	Quality Assurance
QoL	Quality of Life
QoLISSY	Quality of Life in Short Stature Youth
RA	Regulatory Authority
RBC	Red Blood Cells
r-hGH	Recombinant Human Growth Hormone
SAE	Serious Adverse Event
SAP	Statistical Analysis Plan
SC	Subcutaneous
Scr	Serum Creatinine
SD	Standard Deviation
SDS	Standard Deviation Score
SE	Standard Error
SGA	Small for Gestational Age
SHOX	Short stature homeobox
SmPC	Summary of Product Characteristics
SOC	System Organ Class
SOP	Standard Operating Procedure
SUSAR	Suspected Unexpected Serious Adverse Reaction
t	Time
t 1/2	Half-life
Tmax	Time Of Maximum Concentration
TSH	Thyroid Stimulating Hormone
UK	United Kingdom
USA	United States of America
USAN	United States Adopted Name
vs	Versus
WBC	White Blood Cells
WHO	World Health Organization
wk	Week

## 1. INTRODUCTION

### 1.1 GROWTH HORMONE DEFICIENCY

Human growth hormone (hGH) is a 191-amino-acid pituitary protein that stimulates hepatic production and release of IGF-1 into the systemic circulation. IGF-1 is an important mediator in the promotion of linear growth in children and may play a role in the regulation of metabolism and body composition in adults. These factors are regulated through complex feedback mechanisms involving hGH, IGF-1 and their complexes (Shalet, Toogood et al. 1998; Bach 2004).

A GHD results in inadequate circulating IGF-1 levels and is manifested as abnormal linear growth in children (Krysiak, Gdula-Dymek et al. 2007; Thomas and Monson 2009).

Childhood GHD can be congenital, acquired, or idiopathic. Underlying causes for congenital malformation include pituitary dysfunction due to abnormal neurodevelopment *in utero* of certain brain regions and genetic abnormalities. Etiology for acquired GHD includes brain tumors in the hypothalamic region, traumatic brain injury, infiltrative disease, cranial irradiation and surgical intervention. The idiopathic origin of GHD is poorly understood but it appears to be multifactorial (Rona and Tanner 1977).

Data on incidence and prevalence rates of GHD are scarce. A nationwide study in Denmark reported average incidence rate of 2.58 males, and 1.7 females per 100,000 population for childhood onset of GHD (Stochholm, Gravholt et al. 2006). The prevalence and demographics of childhood GHD in Belgium during the period 1986-2001 was estimated to be 1/5600. The origin of GHD was idiopathic in 41% of the patients, congenital in 20% and acquired in 7%; there was male predominance in all 3 categories (Thomas, Massa et al. 2004). The number of new cases has remained fairly constant over the last 2 decades. The Belgian data are comparable to other countries; the prevalence of GHD in the USA in the 1990's was at least 1:3480, with male predominance (Lindsay, Feldkamp et al. 1994).

Most morbidity in children with GHD relates to short stature. The inability to achieve normal Ht can lead to early onset of severe psychosocial problems directly related to short stature. This is confounded by delayed puberty and deficits in facial, dental and (in males) genital development. Approximately 5% of children with GHD have episodes of hypoglycemia, particularly in infancy (Krysiak, Gdula-Dymek et al. 2007). Persistency of GHD into adulthood is associated with increased risk of cardiovascular morbidity and mortality.

